### 7.3 Exclusion Criteria

1. Location of the treatment area
  - on the periorbital skin
  - within 5 cm of an incompletely healed wound
  - within 10 cm of a suspected basal cell carcinoma (BCC) or squamous cell carcinoma (SCC).
2. Previous participation in an ingenol mebutate trial.
3. Treatment with ingenol mebutate gel in the treatment area within 6 months or outside of the treatment area within 30 days prior to study treatment initiation.
4. Receipt of the following within 90 days prior to study treatment initiation:
  - interferons or interferon inducers
  - any dermatologic procedures or surgeries within the treatment area
5. Receipt of any topical prescription medications in the treatment area within 30 days prior to study treatment initiation.
6. Lesions in the treatment area have atypical clinical appearance (e.g. giant lesions greater than 5 mm, eczematous lesions, or folliculocentric lesions).
7. Active dermatologic conditions that may confound the diagnosis of MC or would interfere with assessment of treatment, such as scabies, cutaneous lymphoma, or psoriasis.
8. Clinical diagnosis/history or evidence of any medical condition that would expose a subject to an undue risk of a severe AE or interfere with assessments of safety and efficacy during the course of the trial, as determined by the (sub)investigator's clinical judgment.
9. Known history of infection with Human Immunodeficiency Virus (HIV).
10. History of melanoma.
11. History of chronic alcohol or drug abuse within 12 months prior to screening, or any condition associated with poor compliance as judged by the (sub)investigator.
12. Known or suspected allergy or reaction to any component of the IMP formulation.
13. Patients who have experienced a clinically important medical event within 90 days prior to study treatment initiation (e.g., stroke, myocardial infarction, etc).
14. Pregnant, breastfeeding, or lactating women.
15. Participation in any another interventional clinical trial within 30 days prior to study treatment initiation.

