### 5.2 Secondary Endpoints

- Partial clearance at Week 4, defined as at least 50% reduction in the number of clinically visible MCs in the treatment area

- Percentage of subjects who sustain complete clearance of MCs in the treatment area at Week 24
- Percentage of subjects who clear MCs outside of the treatment area at Week 24

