### 7.2 Inclusion Criteria

1. Signed and dated informed consent has been obtained.
2. Male or non-pregnant female at least 18 years of age.
3. Subject must have an immunocompromised condition due to use of immunosuppressive therapies for cancer or autoimmune disease treatment or prevention of organ transplant rejection or due to an inherited condition that affects the immune system.
4. Subject has at least 10 clinically typical, visible and discrete MCs within a treatment area on either the face and/or trunk. Treatment area is defined as either:
  - One contiguous treatment area of at most 100 cm^2
  - Two non-contiguous treatment areas totaling at most 100 cm^2
5. Subject must be willing to forego any other treatments of MC on the face and/or trunk, including tanning bed use and excessive sun exposure, throughout the duration of the trial.
6. Subject is willing and able to participate in the study as an outpatient, making frequent visits to the study center during the treatment and follow-up periods, and to comply with all study requirements.
7. Female subjects of childbearing potential\* must have a negative urine pregnancy test prior to trial treatment.

\* A female is defined as not being of child-bearing potential if she is postmenopausal (at least 12 months with no menses without an alternative medical cause prior to screening) or surgically sterile (hysterectomy, bilateral salpingectomy or bilateral oophorectomy).

8. Female subjects of childbearing potential must be willing to use effective contraception at trial entry and until the last follow-up visit at Week 24.

Effective contraception is defined as follows:

- Abstinence (when this is in line with the preferred and usual life style of the subject).
- Vasectomized partner (given that the subject is monogamous).
- An intrauterine device.
- Double barrier method defined as condom in combination with diaphragm
- Hormonal contraceptive (oral hormonal birth control, estrogenic vaginal ring, percutaneous contraceptive patches, implants and injectables) for at least one menstrual cycle prior to enrollment.

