**Panel 2 Schedule of trial procedures: second and third course of treatment**

	Second course of treatment 				Third course of treatment 			
Visit Number	6	7	8	9	10	11	12	13
Week	5	6	7	8	9	10	11	12
Day	35	42	49	56	63	70	77	84
Visit Window	±3 days	±3 days	±3 days	±3 days	±3 days	±3 days	±3 days	±3 days
Informed consent								
Inclusion/Exclusion								
Demographics								
Medical history								
Medication history								
Vital signs								
Height and weight								
Physical examination 					X			X
Urine pregnancy test 	X	X	X	X	X	X	X	X
Dermatological Assessment (Diagnosis)								
MC lesion count	X	X	X	X	X	X	X	X
LSR assessment	X	X	X	X	X	X	X	X
Adverse event(s)	X	X	X	X	X	X	X	X
Concomitant medications/procedures 	X	X	X	X	X	X	X	X
PROs and Questionnaires 					X			X
Subject instruction/Diary review	X	X	X	X	X	X	X	X
Dispense medication/diary				X 				
Collect medication/diary	X				X			
Assess subject compliance	X	X	X	X	X	X	X	X

- 1) Screening and baseline visit will be done on the same day. There will be no washout period.
- 2) Abbreviated physical examination including general appearance, regional lymph nodes and dermatologic examination of the skin.
- 3) Only female subjects of child-bearing potential.

- 4) At Visit 1, procedures should be recorded as Medical/Surgical History.
- 5) Patient reported outcomes (PROs) and questionnaires include EQ-5D-5L and TSQM v.9.
- 6) Additional IP will be dispensed at Week 4 and/or Week 8 for subjects who have incomplete clearance of MC in the treatment area.
- 7) A second course of treatment is warranted only for subjects who have incomplete clearance MC in the treatment area at Week 4.
- 8) A third course of treatment is warranted only for subjects who have incomplete clearance MC in the treatment area at Week 8.
- 9) For unscheduled visits, only assessments that require follow-up will be conducted.

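### Apart from three named exceptions, the look-back windows cover only prescription topicals and procedures inside the treatment area, so earlier treatment of outside lesions can count as gel efficacy at Week 24

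*Protocol*

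**What the plan says.** Protocol Section 7.3 sets five look-backs that bear on earlier treatment:

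- Exclusion 3: "Treatment with ingenol mebutate gel in the treatment area within 6 months or outside of the treatment area within 30 days" before treatment starts.
- Exclusion 4, first item: "interferons or interferon inducers", 90 days, with no limit on body site.
- Exclusion 4, second item: "any dermatologic procedures or surgeries within the treatment area", 90 days.
- Exclusion 5: "Receipt of any topical prescription medications in the treatment area within 30 days prior to study treatment initiation".
- Exclusion 15: "Participation in any another interventional clinical trial within 30 days prior to study treatment initiation".

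Sections 6.1 and 8.1 put screening and baseline on the same day, and the footnotes to the schedule add "There will be no washout period". The first application is that night. Inclusion 5 in Section 7.2 reads "Subject must be willing to forego any other treatments of MC on the face and/or trunk", but it binds only for the duration of the trial.

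The endpoints in Sections 5.1 and 5.2 are complete and partial clearance in the treatment area at Week 4, sustained clearance there at Week 24, and "Percentage of subjects who clear MCs outside of the treatment area at Week 24". Section 3.3 presents the last of these as evidence of long-term efficacy. The design is an uncontrolled case series of 10 subjects (Sections 6.1 and 6.2).

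**The concern.** With no run-in and no comparator, a lesion already responding to something else on Day 0 looks the same as one that responds to the gel. It is counted at baseline, disappears later, and is scored as clearance. A rule on treatment during the trial cannot repair this, because the other treatment was given before baseline.

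The protocol accepts that recent treatment matters, since it sets windows of 30 days, 90 days and 6 months. The question is whether those windows cover the lesions on which each endpoint is scored. For lesions outside the treatment area they mostly do not, and the Week 24 outside-area percentage is scored on exactly those lesions.

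**Working it through.** The protocol gives no figure to reproduce: Section 6.2 states 10 subjects without a calculation. The check sets the eligibility text against the endpoints and then scales the effect.

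**Step 1. Which earlier MC treatments have a look-back?** (Section 7.3)

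| Earlier treatment | Inside the area | Outside the area |
|---|---|---|
| Ingenol mebutate | 6 months | 30 days |
| Interferons or inducers | 90 days | 90 days |
| Any treatment within another interventional trial | 30 days | 30 days |
| Procedure or surgery | 90 days | none |
| Prescription topical other than ingenol mebutate | 30 days | none |
| Non-prescription topical | none | none |
| Systemic MC treatment other than interferons or inducers | none | none |

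**Step 2. Does another provision close the empty cells?**

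- Inclusion 5 looks forward only.
- Exclusion 8 concerns medical conditions, not earlier treatment.
- Section 8.5 records MC treatment history and whether it was in the treatment area, but excludes nobody and does not ask for dates. Section 8.10 asks for dates of procedures and of medication used during the trial. Panel 1 lists a medication history at Visit 1 without describing its content.
- Inclusion 4 requires at least 10 typical, visible MCs in the area on Day 0. This shows that lesions are present, not that they are untreated. No minimum number of lesions applies outside the area.

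**Step 3. Which endpoints are reached?** The outside column has four empty cells and feeds the Week 24 outside-area endpoint. The inside column has two and feeds the Week 4 endpoints.

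**Step 4. Scale.** One carried-over clearance moves a percentage by 100/m points, where m is the denominator.

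- Week 4, m = 10: 100/10 = 10 points. This is a maximum per subject, reached only if the subject would otherwise have been a failure.
- Outside area: m is the number of subjects with outside MCs at baseline, which the protocol does not fix. At m = 10 the step is 10 points; at an assumed m = 5 it is 100/5 = 20 points.

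**Step 5. How likely is at least one such subject?** The share p with recent, uncovered MC treatment is not given. The chance of at least one among 10 is 1 − (1 − p)^10:

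| Assumed p | Chance of at least one in 10 |
|---|---|
| 5% | 1 − 0.95^10 = 40% |
| 10% | 1 − 0.90^10 = 65% |
| 20% | 1 − 0.80^10 = 89% |
| 30% | 1 − 0.70^10 = 97% |

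These are chances that a recently treated subject is enrolled, not that the earlier treatment produces a clearance.

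**The case against.** The strongest reply is that the protocol already does most of the work. Inside the area, prescription topicals, procedures, interferons or inducers and ingenol mebutate are all covered. To alter the Week 4 primary result, an uncovered agent would have to leave at least 10 typical lesions on Day 0 and then clear every one by Week 4 where the gel would not have. Exclusion 6 bars atypical lesions, Exclusion 1 bars areas close to an incompletely healed wound, and the in-area count takes only typical MCs (Section 8.14). Section 3.1 adds that MC in these patients often resists conventional treatment. This stands, and it makes the Week 4 gap narrow. It does not help outside the area, where there is no minimum count and no typical-lesion requirement is stated.

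Three stronger readings are tempting and are not supported:

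- A reader might infer that the windows cover nothing except in-area prescription topicals and procedures. Exclusions 3, 4 (interferons or inducers) and 15 show otherwise, and all three also reach outside the area.
- A reader might assume that 1 to 3 of the 10 subjects were recently treated and infer a shift of 10 to 30 points. That share appears nowhere in the protocol, and the shift would need every such subject to change from failure to clearance solely because of the earlier treatment. It is a ceiling on an assumption.
- A reader might apply 10 points per subject to the outside-area rate. Its denominator need not be 10.

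It can also be said that handling of recently treated subjects belongs in an analysis plan. That is fair for the outside-area endpoint, but such a rule needs treatment dates. Section 8.5 does not ask for them, and eligibility itself is fixed in the protocol.

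**Conclusion.** The point holds in a limited form. Followed as written, the protocol lets MCs outside the treatment area be treated by a procedure, or by a topical other than ingenol mebutate, up to Day 0, and then counts their clearance as gel efficacy at Week 24. That endpoint carries most of the weight. A smaller exposure remains for the Week 4 endpoints, through non-prescription topical or non-interferon systemic MC treatment, softened by the requirement for 10 typical visible lesions.

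The size of the bias cannot be computed from the protocol. What can be said is the step per affected subject: at most 10 points at Week 4, and more than 10 for the outside-area rate if fewer than 10 subjects have outside lesions at baseline. The conclusion rests on the text of Sections 7.2, 7.3, 8.1 and 8.5 and on the absence of a control arm. It does not depend on any assumed share of recently treated subjects. The change is worth making because it is cheap and because nothing in a single-arm series can separate the two effects afterwards.

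**What to change.** 1. Extend Exclusion 5 to any MC-directed treatment of lesions in the treatment area, topical or systemic, prescription or not. Keep the existing 30 days, with the sponsor confirming whether that window suits systemic agents; this is a clinical decision that the protocol does not settle. Simply deleting the word prescription would also bar topicals unrelated to MC, which is not needed.
2. Under Section 8.5, record the dates and location of prior MC treatment. Restrict the outside-area endpoint to subjects who have outside MCs at baseline and whose outside lesions received no MC-directed topical within 30 days, or procedure within 90 days, before Day 0. Both periods are the protocol's own. This leg excludes nobody from the trial.

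Cost: a reworded criterion, an added history item and one sentence on the endpoint. Section 7.1 bars re-screening after a failed criterion, so a consented candidate who fails the wider Exclusion 5 is lost rather than delayed. Checking treatment history before consent would largely avoid that. The outside-area denominator may shrink slightly.

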### 7.4 Subject Screening Log

As a minimum, subjects who have signed the informed consent form but who are not necessarily assigned to trial treatment, should be registered on the log.

### 7.5 Subject Identification List

The (sub)investigator must maintain a list of all subjects enrolled in the trial site including each subject's identity, date of enrollment and corresponding subject ID so that any subject may be identified if required for any reason. The list is kept by the investigator and must not be copied or retained by LEO.

At Visit 1 each subject must be assigned a unique subject ID to protect the subject's identity and which will be used in lieu of the subject's name when the (sub)investigator reports trial related data.

## 7.6 Withdrawal criteria

Subjects **may** withdraw from the trial for any of the following reasons:

1. *Unacceptable treatment efficacy*: the (sub)investigator is free to withdraw the subject at any time based on a medical judgement.
2. *Unacceptable AEs/LSRs*: any AEs or LSRs that the (sub)investigator or the subject considers unacceptable.
3. *Exclusion criteria*: any exclusion criteria which emerge/become apparent during the subject's participation in the clinical trial.
4. *Voluntary withdrawal*: subjects are free to withdraw from the clinical trial at any time and for any reason. If applicable, the subject's legal representative can withdraw the subject from the trial.
5. *Other reasons*: other reasons than stated above which require the subject to (be) withdraw(n) should be specified.
6. *Lost to follow-up*.
7. *Death*.

Subjects who are discovered, after enrollment, not to have fulfilled all in- /exclusion criteria at the time of enrollment should discontinue treatment unless the (sub)investigator, based on clinical and ethical evaluation, finds discontinuation inappropriate.

Subjects who discontinue treatment for any reason should remain in the trial until Week 24. All subjects should as a minimum be asked to complete the final efficacy assessment that correlates with their treatment course (Week 4, Week 8 or Week 12) and the final visit at Week 24. For subjects withdrawn from treatment or trial, AEs should be followed up as described in Section 9. Subjects withdrawn can be substituted.

Reason(s) for discontinuation from IMP and withdrawal from the trial must be recorded in the medical records (lack of efficacy, AE, withdrawal by subject, lost to follow-up, death, other).

### Lost to follow-up

A subject will be considered lost to follow-up if they repeatedly fail to return for scheduled visits and if the trial site is not able to get in contact with the subject.

The following actions must be taken if a subject fails to return to the trial site for a required visit:

- The trial site must attempt to contact the subject and reschedule the missed visit as soon as possible and counsel the subject on the importance of maintaining the assigned visit schedule and ascertain whether or not the subject wishes to and/or should continue in the trial.
- Before a subject is deemed lost to follow-up, the investigator or designee must make every effort to regain contact with the subject (where possible, 3 telephone calls and, if necessary, a certified letter to the subject's last known mailing address or local equivalent methods). These contact attempts should be documented in the subject's medical record.
- Should the subject continue to be unreachable, they will be considered to have withdrawn from the trial with a primary reason of lost to follow-up.

## **8 Trial Schedule and Assessments**

### **8.1 Schedule of Trial Procedures**

**Panel 1 Schedule of trial procedures: first course of treatment and follow-up period**

	Screening/Baseline 	First course of treatment				Follow-up period			
Visit Number	1	2	3	4	5	14	15	16	Unscheduled/ Early Term 
Week	0	1	2	3	4	16	20	24	N/A
Day	0	7	14	21	28	112	140	168	N/A
Visit Window	N/A	±3 days	±3 days	±3 days	±3 days	±3 days	±3 days	±3 days	N/A
Informed consent	X								
Inclusion/Exclusion	X								
Demographics	X								
Medical history	X								
Medication history	X								
Vital signs	X								
Height and weight	X								
Physical examination 	X				X				X
Urine pregnancy test 	X	X	X	X	X	X	X	X	X
Dermatological Assessment (Diagnosis)	X								
Identification of treatment area	X								
MC lesion count	X	X	X	X	X	X	X	X	X
LSR assessment	X	X	X	X	X	X	X	X	X
Adverse event(s)	X	X	X	X	X	X	X	X	X
Concomitant medications/procedures 	X	X	X	X	X	X	X	X	X
PROs and Questionnaires 	X	X	X	X	X	X	X	X	X
Subject instruction/Diary review	X	X	X	X	X	X	X	X	X
Dispense medication/diary	X				X 				
Collect medication/diary		X							
Assess subject compliance		X	X	X	X	X	X	X	X

**Panel 2 Schedule of trial procedures: second and third course of treatment**

	Second course of treatment 				Third course of treatment 			
Visit Number	6	7	8	9	10	11	12	13
Week	5	6	7	8	9	10	11	12
Day	35	42	49	56	63	70	77	84
Visit Window	±3 days	±3 days	±3 days	±3 days	±3 days	±3 days	±3 days	±3 days
Informed consent								
Inclusion/Exclusion								
Demographics								
Medical history								
Medication history								
Vital signs								
Height and weight								
Physical examination 					X			X
Urine pregnancy test 	X	X	X	X	X	X	X	X
Dermatological Assessment (Diagnosis)								
MC lesion count	X	X	X	X	X	X	X	X
LSR assessment	X	X	X	X	X	X	X	X
Adverse event(s)	X	X	X	X	X	X	X	X
Concomitant medications/procedures 	X	X	X	X	X	X	X	X
PROs and Questionnaires 					X			X
Subject instruction/Diary review	X	X	X	X	X	X	X	X
Dispense medication/diary				X 				
Collect medication/diary	X				X			
Assess subject compliance	X	X	X	X	X	X	X	X

- 1) Screening and baseline visit will be done on the same day. There will be no washout period.
- 2) Abbreviated physical examination including general appearance, regional lymph nodes and dermatologic examination of the skin.
- 3) Only female subjects of child-bearing potential.

- 4) At Visit 1, procedures should be recorded as Medical/Surgical History.
- 5) Patient reported outcomes (PROs) and questionnaires include EQ-5D-5L and TSQM v.9.
- 6) Additional IP will be dispensed at Week 4 and/or Week 8 for subjects who have incomplete clearance of MC in the treatment area.
- 7) A second course of treatment is warranted only for subjects who have incomplete clearance MC in the treatment area at Week 4.
- 8) A third course of treatment is warranted only for subjects who have incomplete clearance MC in the treatment area at Week 8.
- 9) For unscheduled visits, only assessments that require follow-up will be conducted.

## 8.2 Subject Eligibility

Refer to Sections 7.2 and 7.3.

## 8.3 Demographics

Subject demographics will be recorded at Visit 1. The following will be recorded:

- Date of birth
- Sex
- Race: American Indian or Alaska Native; Asian, Black or African American; Native Hawaiian or Other Pacific Islander; White; Other
- Ethnic origin (self-reported by the subject): Hispanic or Latino, not Hispanic or Latino

## 8.4 Height and Weight

The subject's height must be measured or self-reported (cm or inches) and weight must be determined or self-reported (kg or pound) at Visit 1.

## 8.5 Medical/Surgical History

Medical history must be recorded at Visit 1:

- Skin disease history
- MC treatment history
- Other medical/surgical history within the previous 12 months

It must be recorded if the skin disease or the MC treatment was within the treatment area.

## 8.6 Physical Examination

An abbreviated physical examination including general appearance, regional lymph nodes and dermatologic examination of the skin must be performed at visits indicated in Section 8.1.

## 8.7 Vital Signs

Blood pressure and heart rate must be assessed after approximately 5 minutes in a sitting position at visits indicated in Section 8.1.

## 8.8 Pregnancy Test

In female subjects of child-bearing potential a urine pregnancy test must be performed at the trial site at visits indicated in Section 8.1.

## 8.9 Dermatological Assessments (Diagnosis)

Assessment and diagnosis of molluscum contagiosum must be confirmed by the sub(investigator) prior to study treatment initiation.

## 8.10 Concomitant Medications and Procedures

Concomitant medication is defined as any medication used by a subject during the clinical trial apart from the IP.

Use of concomitant medication must be recorded in the subject's medical record (treatment/drug name, total daily dose, indication and dates of start and stop) at visits indicated in Section 8.1. For topical treatment it must be recorded if the treatment is within 5 cm (appr. 2 inches) of the treatment area.

Procedures including body location, diagnosis, start/stop date must be recorded at visits indicated in Section 8.1. It must also be recorded if the procedure is inside the treatment area. Procedures reported by the subject at Visit 1, should be recorded as medical/surgical history.

